1.3. Known and Potential Benefits and Risks to Patients

1.3.1. Known and Potential Benefits and Risks of the Test Investigational Medicinal Product(s)

Additional information regarding benefits and risks to patients may be found in the IB.

1.3.1.1. Identified Risks

1.3.1.1.1. General Disorders and Administrative Site Conditions

Reports of transient administration site reactions, including injection site bruising, injection site swelling, injection site pain, injection site pruritus, injection site induration, injection site erythema, injection site inflammation, injection site warmth, injection site dermatitis, injection site rash, injection site edema, injection site discomfort, injection site hemorrhage, injection site irritation, injection site mass, and injection site hematoma, have occurred with sc administration. Among these events, the following have been identified as adverse drug reactions (identified risks): injection site erythema, injection site induration, injection site pruritus, injection site pain, and injection site rash. None of the identified risks were considered important risks.

1.3.1.1.2. Injury, Poisoning, and Procedural Complications/Immune System Disorders

The general risks of infusion reactions with monoclonal antibody administration include fever, headache, nausea, vomiting, and hypotension. These adverse events are generally ascribed to lysis of cellular targets, cytokine release, or complement activation.

Type I hypersensitivity or allergic reactions (eg, shortness of breath, urticaria, anaphylaxis, and angioedema) are theoretically possible with any injected protein.

Type III hypersensitivity reactions occur as a consequence of an antibody response to the injected protein resulting in immune complex formation. Such immune complex formation and subsequent deposition in tissues may result in symptoms, including rash, urticaria, polyarthritis, myalgias, polysynovitis, fever, neuritis, or angioedema, and if untreated and severe, can progress to glomerulonephritis.

Infusion-related reaction and drug hypersensitivity have occurred rarely with fremanezumab. In all patients in the placebo controlled studies, drug hypersensitivity occurred in 2 patients (<1%) who received placebo and 2 patients (<1%) who received fremanezumab (1 moderate event and 1 mild event). Among all fremanezumab-treated patients, 3 additional patients who received fremanezumab had adverse events of drug hypersensitivity (2 moderate events and 1 mild event).

1.3.1.2. Potential Risks

1.3.1.2.1. Perivascular Inflammation

In the 3-month monkey toxicology study, inflammation around the ciliary vessel of the eye was observed. Based on the low-grade increase in immune complex deposits observed in the intima and/or media of ciliary vessels in the animals with perivascular inflammation, these events were assessed as being due to the monkeys' immunogenic response to humanized monoclonal antibody rather than a pharmacologic toxicity and are not likely to be relevant in a clinical setting. Moreover, a confirmatory 6-month study could not repeat the findings.

1.3.1.2.2. Consequences of Calcitonin Gene-Related Peptide Inhibition

Because CGRP is a vasodilator, there is a theoretical risk of unfavorable cardiovascular effects with CGRP inhibition. Extensive research conducted with the CGRP receptor antagonists has not identified relevant safety cardiovascular concerns in humans. Dedicated studies conducted in monkey and humans using fremanezumab have not identified clinically relevant changes in heart

rate, blood pressure, or other cardiovascular parameters. No relevant cardiovascular event has been seen in the completed studies.

1.3.2. Overall Benefit and Risk Assessment for This Study

In summary, the benefit and risk assessment for fremanezumab is favorable following review of the available safety and efficacy data.

2. STUDY OBJECTIVES AND ENDPOINTS

2.1. Primary and Secondary Study Objectives and Endpoints

The primary and secondary study objectives and endpoints are in [Table 3](#):

Table 3: Primary and Secondary Study Objectives and Endpoints

Objectives	Endpoints

Primary objective: To evaluate the efficacy of monthly 225 mg subcutaneous (sc) fremanezumab in adult patients with migraine and major depressive disorder (MDD)
	
Mean change in the monthly average number of migraine days from the 28-day baseline period during the 12-week period after the first dose of study drug

Key secondary objective: To evaluate the efficacy of monthly 225 mg sc of fremanezumab in adult patients with migraine and MDD on the reduction of MDD symptoms
	
Mean change in depression symptoms from randomization (day 1) to week 8 after the first dose of study drug as measured by:
 
 • Hamilton Depression Rating Scale-17 items (HAM-D 17)

Secondary objective: To evaluate the efficacy of monthly 225 mg sc fremanezumab in adult patients with migraine and MDD in terms of responder rates in monthly migraine days
	
Number of patients with 50% or more reduction from the 28-day baseline period in the monthly average number of migraine days at 12 weeks after the first dose of study drug

Secondary objective: To evaluate the efficacy of monthly 225 mg sc fremanezumab in adult patients with migraine and MDD in terms of improving quality of life
	
Mean change in quality of life from randomization visit (day 1) to week 12 after the first dose of study drug as measured by:
 
 • Migraine-Specific Quality of Life (MSQoL) questionnaire, role function-restrictive and role function-preventive domains

Table 3: Primary and Secondary Study Objectives and Endpoints (Continued)

Objectives	Endpoints

Secondary objective: To evaluate the efficacy of monthly 225 mg sc fremanezumab in adult patients with migraine and MDD in terms of improving disability
	
Mean change from randomization visit (day 1) in disability score for overall impact as measured by Clinical Global Impression-Severity (CGI-S) and 6-item Headache Impact Test (HIT-6) to the following time points after administration of the first dose of study drug:
 
 • weeks 4 and 8 (CGI-S) • week 12 (CGI-S and HIT-6)

Safety and tolerability objective (Secondary objective): To evaluate the safety and tolerability of monthly 225 mg sc and quarterly 675 mg sc fremanezumab in adult patients with migraine and MDD
	
 • occurrence of adverse events throughout the study • changes from randomization visit (day 1) in vital signs (pulse, systolic and diastolic blood pressure, body temperature, and respiratory rate) measurements • abnormal physical examination findings including body weight • use of concomitant medication for adverse events during the study • number (%) of patients who did not complete the study due to adverse events • occurrence of severe hypersensitivity/anaphylaxis reactions • suicidal ideation and behavior as suggested by eC-SSRS

CGI-S = Clinical Global Impression-Severity; eC-SSRS = electronic Columbia-Suicide Severity Rating Scale; HAM-D 17 = Hamilton Depression Rating Scale-17 items; HIT-6 = 6-item Headache Impact Test; MDD = major depressive disorder; MSQoL = Migraine-Specific Quality of Life; sc = subcutaneous.

2.1.1. Justification of Primary Endpoint

The primary endpoint was chosen based on the International Headache Society (IHS) guidelines for trials in migraine, which suggest that the most appropriate primary endpoint to capture efficacy of treatment is the change from baseline in the monthly average number of migraine days ([Silberstein, 2008](#)).

2.2. Exploratory Objective and Endpoints

[REDACTED]

- [REDACTED]

- [REDACTED]

- [REDACTED]

- [REDACTED]

- [REDACTED]

- [REDACTED]

- [REDACTED]

- [REDACTED]

- [REDACTED]

- [REDACTED]

- [REDACTED]

3. STUDY DESIGN

3.1. General Study Design and Study Schematic Diagram

This is an approximately 28-week, multicenter, randomized, double-blind, placebo investigational medicinal product (IMP)-controlled, parallel-group study to evaluate the efficacy and safety of fremanezumab self-administered at monthly doses of 225 mg sc and a quarterly dose of 675 mg sc (ie, one dose using 3 prefilled syringes with 225 mg each) in adult patients with migraine and MDD. The study will consist of a 28-day (ie, 4-week) baseline period, a 12-week double-blind treatment phase followed by a 12-week open-label extension phase, and an end-of-treatment visit (approximately 12 weeks after the final dose of study drug).

The total duration of patient participation in the study is planned to be approximately 28 weeks. Patients are expected to complete the entire duration of the study.

This study will include female and male patients, aged 18 to 70 years, inclusive, with a diagnosis of migraine and MDD. Patients must have been diagnosed with migraine at least 12 months prior to the screening visit (visit [V] 1). The diagnosis of migraine (as defined by the International Classification of Headache Disorders, 3rd revision [ICHD-3] criteria [IHS, 2013], see [Appendix I](#)) will be prospectively confirmed via a review of migraine data recorded daily during a 28-day baseline period in an electronic diary device. Patients must also have a history of MDD according to the Fifth Edition of the Diagnostic and Statistical Manual of Mental Disorders (DSM-V) criteria at least 12 months prior to the screening visit (V1) and have active symptoms of depression as assessed by a PHQ-9 score of at least 10 at screening. Investigators must document that patients had the diagnosis of migraine and MDD for at least 12 months prior to the screening visit (V1).

During the 28-day baseline period, patients must fulfill the following criteria for migraine:

- on ≥ 4 days, headache attacks qualified as migraine based on the following ICHD-3 criteria:
 - ICHD-3 diagnostic criteria C and D for 1.1 Migraine without aura
 - ICHD-3 criteria B and C for 1.2 Migraine with aura
 - probable migraine (a migraine subtype where only 1 migraine criterion is missing)
 - triptan or ergot derivative used to treat an established headache.

Patients who fulfill the criteria for migraine will be further delineated as patients with CM or EM, for stratification and other analyses.

CM is defined as:

Patient fulfills the following criteria for CM in prospectively collected baseline information during the 28-day baseline period:

- headache occurring on ≥ 15 days

- on ≥ 8 days, fulfilling any 1 of the following:
 - ICHD-3 diagnostic criteria C and D for 1.1 Migraine without aura ([Appendix I](#))
 - ICHD-3 criteria B and C for 1.2 Migraine with aura ([Appendix I](#))
 - probable migraine (a migraine subtype where only 1 migraine criterion is missing)
 - triptan or ergot derivative used to treat established headache.

EM is defined as:

The patient fulfills the following criteria for EM in prospectively collected baseline information during the 28-day baseline period:

- headache occurring ≥ 4 days but < 15
- on ≥ 4 days, fulfilling any 1 of the following:
 - ICHD-3 diagnostic criteria C and D for 1.1 Migraine without aura ([Appendix I](#))
 - ICHD-3 criteria B and C for 1.2 Migraine with aura ([Appendix I](#))
 - probable migraine (a migraine subtype where only 1 migraine criterion is missing)
 - triptan or ergot derivative used to treat an established headache

At the randomization visit (day 1), patients will be randomly assigned to 1 of 2 treatment groups of 225 mg sc fremanezumab or placebo in a 1:1 ratio. Patients will receive their assigned study treatment on visit 2 (day 1), visit 3 (day 29), and visit 4 (day 57) and then continue into the open-label extension phase in which all patients will receive a quarterly dose of 675 mg sc fremanezumab on visit 5 (day 85). Investigators can contact patients in between study visits per their clinical judgment.

[figure not shown]
Patients who complete all scheduled visits will have procedures and assessments performed at visit 6 (end of treatment). Patients who withdraw from the study before completing the 24-week treatment phase will have visit 6 (end of treatment) procedures and assessments performed at their final visit.

Study procedures and assessments with their time points are shown in [Table 4](#). The study schematic diagram is shown in [Figure 1](#).

The end of study is defined as the last visit (end-of-treatment/early withdrawal visit [visit 6]) of the last patient.

The study duration will be approximately 24 months, from approximately September 2019 (first patient screened) to approximately August 2021 (last visit of the last patient).

Figure 1: Overall Study Schematic Diagram

EOT = end of treatment; PBO = placebo; sc = subcutaneous; V = visit.

A red circle indicates a study site visit when study medication is self-administered. A blue square indicates a study site visit when study medication is not administered.

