For migraine, patients using no more than 1 preventive medication at the time of the screening visit (V1) will be allowed to remain on the medication. The total number of patients receiving concomitant migraine preventive medication during the study will not exceed 30% of the total sample size of the study. For depression, patients using no more than 1 medication for the treatment of depression at the time of the screening visit (V1) will be allowed to remain on the medication. Patients on a concomitant migraine preventive medication and/or an antidepressant must be on a stable dose for at least 8 weeks of consecutive use prior to study entry (ie, before the 28-day baseline period), without anticipated changes during the study. If in the clinical judgment of the investigator or qualified psychiatrist, the patient's antidepressant medication needs to be changed or dose-adjusted during the 28-day baseline period, the patient will be screen failed. Any changes made during the treatment period will be recorded in the electronic data capture system. The percentage of patients with these changes will be analyzed at the end of the study.

All concomitant medications prescribed or over-the-counter medications, vitamins, or herbal or nutritional supplements, must be recorded with indication, daily dose, and start and stop dates of administration. All patients will be questioned about concomitant medication use at each visit. Complete discontinuation criteria are provided in the full protocol in Section 4.3.

During the 28-day baseline period, patients must fulfill the following criteria for migraine:

- on ≥ 4 days, headache attacks qualified as migraine based on the following ICHD-3 criteria:
 - ICHD-3 diagnostic criteria C and D for 1.1 Migraine without aura
 - ICHD-3 criteria B and C for 1.2 Migraine with aura
 - probable migraine (a migraine subtype where only 1 migraine criterion is missing)
 - triptan or ergot derivative used to treat an established headache

Patients who fulfill the criteria for migraine will be further delineated as patients with chronic migraine (CM) or episodic migraine (EM), for stratification and other analyses.

CM is defined as:

Patient fulfills the following criteria for CM in prospectively collected baseline information during the 28-day baseline period:

- headache occurring on ≥ 15 days
- on ≥ 8 days, fulfilling any 1 of the following:

- ICHD-3 diagnostic criteria C and D for 1.1 Migraine without aura ([Appendix I](#))

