4.1. Patient Inclusion Criteria

Patients may be randomized/enrolled in this study only if they meet all of the following criteria:

- a. The patient is capable of giving signed informed consent, which includes compliance with the requirements and restrictions listed in this protocol.
- b. The patient is male or female and 18 to 70 years of age, inclusive.
- c. The patient has a diagnosis of migraine with onset at ≤ 50 years of age.
- d. Prior to the screening visit (V1), the patient has a 12-month history of either:
 - migraine (according to ICHD-3 criteria [[IHS, 2013](#)]) or
 - headache consistent with migraine (ie, migraine diagnosis not better accounted for by another ICHD-3 diagnosis)
- e. [Revision 1] The patient fulfills the following criteria for migraine in prospectively collected baseline information during the 28-day baseline period:
 - on ≥ 4 days, headache attacks qualified as migraine based on the following ICHD-3 criteria:
 - ICHD-3 diagnostic criteria C and D for 1.1 Migraine without aura
 - headache has at least 2 of the following 4 characteristics: unilateral location; pulsating quality; moderate or severe pain intensity; and aggravation by, or causing avoidance of, routine physical activity (eg, walking or climbing stairs)
 - during headache, at least one of the following: nausea and/or vomiting; photophobia and phonophobia
 - ICHD-3 criteria B and C for 1.2 Migraine with aura
 - 1 or more of the following fully reversible aura symptoms: visual, sensory, speech and/or language, motor, brainstem, retinal
 - at least 2 of the following 4 characteristics: at least 1 aura symptom spreads gradually over ≥ 5 minutes, and/or 2 or more symptoms occur in succession; each individual aura symptom lasts 5 to 60 minutes; at least 1 aura symptom is unilateral; the aura is accompanied, or followed within 60 minutes, by headache not better accounted for by another ICHD-3 diagnosis, and transient ischemic attack has been excluded
 - probable migraine (a migraine subtype where only 1 migraine criterion is missing)

- o triptan or ergot derivative used to treat an established headache.
- f. The patient agrees not to initiate any migraine preventive medications (as defined in [Appendix G](#)) during the study. Up to 30% of patients, however, may take such a single medication previously prescribed for the treatment of migraine.

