4.2. Patient Exclusion Criteria

Patients will not be randomized/enrolled in this study if they meet any of the following criteria:

- a. [Revision 1] The patient uses medications containing opioids (including codeine) or barbiturates (including butalbital/aspirin/caffeine [[Fiorinal](#)®], [Actavis plc](#)], butalbital/paracetamol/caffeine [[Fioricet](#)®], [Cardinal Health](#)], or any other combination containing butalbital) on more than 4 days during the 28-day baseline period for the treatment of migraine or for any other reason.

- b. [Revision 1] The patient has failed 4 or more different medication classes to treat depression in their lifetime (Appendix G).
- c. [Revision 1] If in the clinical judgment of the investigator or qualified psychiatrist, the patient's antidepressant medication needs to be changed or dose-adjusted during the 28-day baseline period.
- d. [Revision 1] The patient has used an intervention/device (eg, scheduled nerve blocks, implantable vagal nerve stimulation, and transcranial magnetic stimulation) for migraine or depression during the 2 months prior to screening.
- e. The patient has used electroconvulsive therapy (ECT) at any time.
- f. The patient suffers from constant or nearly constant headache, defined as having headaches for more than 80% of the time he/she is awake, and less than 4 days without headache per month. Daily headache is acceptable if the patient has headaches 80% or less of the time he/she is awake on most days.
- g. [Revision 1] The patient has clinically significant hematological, cardiac, renal, endocrine, pulmonary, gastrointestinal, genitourinary, neurologic, hepatic, ocular disease, or complications of an infection, at the discretion of the investigator.
- h. [Revision 2] The patient has a clinical history of a severe or uncontrolled psychiatric disorder, to include the following, or at the discretion of the investigator for any clinically significant psychiatric history that would likely interfere with full participation in the study:
 - Lifetime exclusion: suicide attempt
 - In the past 6 months exclusion: suicidal ideation, or other psychoactive spectrum disorders including schizoaffective disorder, delusional disorder, depression with psychotic features, and catatonic disorder

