5.9. Randomization and Blinding

After the 28-day baseline period, the first 12 weeks of this study will be double-blind. Patients and investigators will remain blinded to IMP assignment during this part of the study. This will be followed by a 12-week open-label extension phase.

Patients will receive 225 mg sc fremanezumab (visit 2, visit 3, and visit 4) or matching placebo (visit 2) in monthly doses.

For the first phase of this study, the sponsor, investigators, study staff, and patients will be blinded to treatment assignment. A computer-generated master randomization list will be provided to drug packaging facilities. The packaging vendor(s) will package active drug and placebo into single-visit kits according to Good Manufacturing Practice procedures. Kits will be identical in appearance and contain 1 prefilled syringe with either active drug or placebo.

Patients will be stratified based on sex, country, migraine classification (ie, CM or EM), and PHQ-9 score category (10 to 14, 15 to 19, and ≥ 20) to ensure balance for the covariates.

Patients will be randomly assigned to treatment groups by means of a computer-generated randomization list using electronic IRT. This system is used to ensure a balance across treatment groups. The specifications for randomization will be under the responsibility and oversight of Teva Global Statistics.

At randomization visit (day 1), each patient will be randomized in a 1:1 ratio within the stratum to which he or she belongs to receive monthly 225 mg sc fremanezumab or placebo, as assigned by the IRT. In the open-label extension phase starting at week 12, however, all patients will receive active treatment with a quarterly dose of 675 mg sc fremanezumab.

The IRT will manage initial drug supply, maintenance of adequate study drug supplies on site, and study randomization centrally. At each study visit where study drug is administered, the IRT will be queried, the site personnel will retrieve the study drug from refrigerated storage, and the patient will self-administer treatment with the 1 or 3 prefilled syringes, depending on the study visit, contained in the appropriately numbered kit.

The sponsor's clinical personnel (and delegates) involved in the study will be blinded to the identity of the IMPs until the database is locked for analysis and the IMP assignment is known. However, if a prioritized sample analysis is needed, bioanalytical and clinical pharmacology personnel may be unblinded.

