3. STUDY DESIGN		
3.1. General Study Design and Study Schematic Diagram		
The patient fulfills the following criteria for EM in prospectively collected baseline information during the 28-day baseline	The patient fulfills the following criteria for EM in prospectively collected	Correction to align with screening criteria

Original text with changes shown	New wording	Reason/justification for change
period: 
 • headache occurring ≥46 days but <15 	baseline information during the 28-day baseline period: 
 1. headache occurring ≥4 days but <15 	

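### Do the CM and EM definitions leave some eligible patients without a stratum, and does that matter for the analysis?

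*Protocol*

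**What the plan says.** Inclusion criterion e (Protocol 4.1) sets the migraine entry requirement: "on ≥ 4 days, headache attacks qualified as migraine based on the following ICHD-3 criteria". It gives no upper limit on headache days and does not require the patient to meet either class definition.

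Protocol 3.1 then states: "Patients who fulfill the criteria for migraine will be further delineated as patients with CM or EM, for stratification and other analyses". The synopsis and SAP 2.1 say the same. CM has two conditions: "headache occurring on ≥ 15 days", and at least 8 days that qualify as migraine. EM also has two: "headache occurring ≥ 4 days but < 15", and at least 4 qualifying days.

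The class is one of four stratification factors. Protocol 5.9 says that "each patient will be randomized in a 1:1 ratio within the stratum to which he or she belongs". It is also a factor in the primary ANCOVA (SAP 6.2.2), the MMRM (SAP 6.2.3.1) and the responder logistic model (SAP 6.3.2.2). All three sections specify the stratification factors as randomized. SAP 5.3 tabulates migraine classification both as randomized and separately, and SAP 6.2.3.3 repeats the primary ANCOVA with the actual factors.

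**The concern.** The text promises that every patient who meets the migraine criteria will be CM or EM, yet the two definitions do not cover everyone who meets them. A patient with 16 headache days and 6 qualifying days satisfies criterion e, has too few qualifying days for CM and too many headache days for EM.

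The exclusion for near-constant headache (Protocol 4.2, criterion f) does not remove this group. It covers patients "defined as having headaches for more than 80% of the time he/she is awake, and less than 4 days without headache per month", so a patient with 4 or more headache-free days is outside it.

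On paper, then, the randomization system has to turn away an otherwise eligible patient, which would be an unwritten entry criterion, or assign a class by a rule that the supplied documents do not show. The actual class would be undefined as well. If it were coded as missing, the patient would drop out of the sensitivity analysis meant to check for stratification errors. An undefined level in a factor used for both randomization and the confirmatory models is worth checking.

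**Working it through.** The plan gives no figure for this point. Its sample-size calculation (288 evaluable, 144 per group) makes no use of the CM/EM split. It reproduces adequately: 143 per group for 90% power with a 2-day difference and SD 5.2, and 90.4% power at 144 per group.

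**Size of the gap in the definitions.** Let H be headache days (0 to 28) and M qualifying migraine days (0 to H).

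- Eligible on criterion e: M ≥ 4. Number of (H, M) pairs: sum of (H − 3) for H = 4 to 28 = 1 + 2 + … + 25 = 325.
- CM: H ≥ 15 and M ≥ 8. Sum of (H − 7) for H = 15 to 28 = 8 + 9 + … + 21 = 203.
- EM: 4 ≤ H < 15 and M ≥ 4. Sum of (H − 3) for H = 4 to 14 = 1 + 2 + … + 11 = 66.
- Both: 0. Neither: 325 − 203 − 66 = 56, which is H = 15 to 28 (14 values) × M = 4 to 7 (4 values).

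Exclusion f needs fewer than 4 headache-free days. Since 28 − 24 = 4, it cannot apply for H = 15 to 24, which is 10 × 4 = 40 of the 56 pairs. In the other 16 (H = 25 to 28) it applies only if headache also fills more than 80% of waking time. These are counts of logical combinations, not shares of patients.

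**Which analyses depend on the missing rule.**

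| Analysis | Class used | Loses unclassed patients? |
|---|---|---|
| Primary ANCOVA (SAP 6.2.2) | as randomized | no |
| MMRM (SAP 6.2.3.1), also used for HAM-D 17, MSQoL, CGI-S and HIT-6 | as randomized | no |
| Responder logistic model (SAP 6.3.2.2) | as randomized | no |
| Sensitivity ANCOVA (SAP 6.2.3.3) | actual | only if actual class is left missing |
| Baseline table (SAP 5.3) | both | shown as missing at worst |

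**Worst case for the one exposed model.** The affected share p is not in the documents; 0.5% to 5% is an assumption. If all affected patients were dropped, the standard error would grow by the factor 1/√(1 − p).

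- p = 0.5%: 340 × 0.005 = 1.7 patients; 1/√0.995 − 1 = 0.25%.
- p = 1%: 340 × 0.01 = 3.4 patients; 1/√0.99 − 1 = 0.50%.
- p = 5%: 340 × 0.05 = 17 patients; 1/√0.95 − 1 = 2.6%.

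**Bias.** The class depends only on diary data collected before randomization. Whether the system blocks such a patient or places the patient in either stratum, it does so before treatment is assigned. Any label fixed from baseline data is a legitimate stratification and adjustment variable, so the treatment comparison is not distorted. The baseline number of migraine days is a separate covariate in the model and already carries these patients' low migraine counts.

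**The case for a change.** The strongest argument for a change is that the defect is certain from the text, cheap to correct, and sits in a factor used for randomization and the confirmatory models. The sponsor also appears to have wanted the classes to match eligibility: Amendment 01 changed the lower EM bound, giving the reason "Correction to align with screening criteria". Incomplete diaries can create further cases. Criterion l accepts 21 diary days of 28, and the class definition states no proration. A patient with 21 entries, 15 headache days and 7 qualifying days is unclassed on raw counts, whereas 15 × 28/21 = 20 and 7 × 28/21 = 9.3 would be CM.

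The wording gap stands, and so does the diary example. The amendment entry concerns the lower bound only and says nothing about patients with 15 or more headache days. The step from gap to harm is not shown. It needs such patients to be randomized and their actual class then to be set to missing, and neither document says that would happen. The remark in SAP 5.3 about presenting missing categories is general table language. The randomization specification is held separately, and SAP Appendix B on derivation logic is listed in the contents but is not in the supplied text; either may contain the rule.

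Rewriting the definitions also has a price. Making EM the complement of CM, for example, would label people with 15 or more headache days as episodic, against the description of EM in Protocol 1.1.1. A protocol change at this stage would need a further amendment with approvals as applicable (Protocol Appendix C).

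**Conclusion.** The CM and EM definitions are mutually exclusive but not exhaustive: eligible patients with 15 to 28 headache days and 4 to 7 qualifying days are unclassed as written. This is missing detail that is settled in practice, because the randomization system must enter CM or EM for anyone it randomizes. The natural course for the analyst is to derive the actual class by that same rule and record it with the derivations.

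The primary result, the secondary results and their type I error control do not depend on which label is used. The largest effect found is a 2.6% wider standard error in one sensitivity analysis. That rests on an assumed 5% share and on every such patient being left unclassed, which neither document states. The conclusion assumes only that the class is assigned before allocation, as the baseline diary definition and Protocol 5.9 imply, and that the models use as-randomized factors, as the SAP says. No change to the plan is needed.
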